### **Participant Compensation**

All eligible participants will be paid for their time and effort for participating in this research project. Each participant will be paid \$10 per hour of participation. Participants can receive a maximum of \$420 (14 study visits × 3 hr/visit × \$10/hr). If, for any reason, a participant wishes to stop the session before all the data are collected, he or she will still receive payment for the time of participation, with each partial hour paid as a full hour.

The participant will receive the payment by check from the Loma Linda Veterans Association for Research and Education (LLVARE). Checks will be mailed to the participant

after every study visit in which he or she participates. In order for the participant to be paid for participation, the first and last name, mailing address, and social security number will be provided to LLVARE on a payment form signed by the participant at each visit. Additionally, each participant will complete an IRS W-9 form at the initial visit; this form will be sent to LLVARE, who requires this form in order to report the participant's income received for this participation.

### **Study Timeline**

The experiment will be carried out over the course of 3 years. Disbursement of research funds from NIH is expected to occur on or before 12/1/2015. Participant recruitment and data collection will begin immediately after disbursement of funds. Using a conservative estimate of recruiting one new participant per week, it will take 40 weeks to recruit all 40 participants. The last participant will therefore be tested approximately 15 weeks from that point, for a total of 55 weeks to complete data collection. We will allot an additional 12 months for data collection to account for potential delays in participant recruitment and attrition.

This study consists of one experiment that will last 3 years total. Each participant is expected to complete all study procedures in from 1 to 14 study visits, ideally over a 10-week period. However, we will allow for the visits to take place across a one year period to account for participants needing to miss or reschedule some visits. Additionally, we will allow each subject to make-up a maximum of 2 study visits. All study visits will last between 2-3 hours. Thus, the maximum amount of participation for each participant is 42 hours during a maximum one year window for data collection.

### **Instrumentation**

Standard-of-care screenings and experimental testing will be carried out in a double-walled sound-isolated audiometric chamber adjoined to a single-walled room in the Auditory Research Laboratory, located at the VALLHS. Initial audiometric testing using standard-of-care procedures will be conducted to verify eligibility for the study and will be carried out using standard clinical equipment. A Grason-Stadler (GSI 61) clinical audiometer calibrated to standards (American National Standards Institute, 1996) will be used to deliver the pure-tone signals for threshold testing through Etymotic Research ER-3A insert earphones. Speech audiometry will be achieved by presenting words (pre-recorded or live voice) through insert earphones via the audiometer. A Grason-Stadler Tymptstar Middle Ear Analyzer acoustic-immittance meter will be used for immittance measurements to verify normal middle ear function. A visual inspection of participants' ear canals and tympanic membranes will be performed using a Welch-Allyn otoscope.

Experimental tests will consist of TEOAE testing, word/sentence recognition testing, and an auditory training program (only participants in the Experimental group will undergo the auditory training). For all experimental testing, participants will be seated in the sound booth. TEOAE testing uses an Etymotic Research ER-10D microphone and loudspeaker assembly. The hardware is controlled by a computer-based otoacoustic emissions system (Intelligent Hearing Systems) that interfaces with the MATLAB programming language. The software allows for the selection of sounds, as well as parameters of the testing such as duration, amplitude, and rate of stimulus presentation. For word and sentence testing, pre-recorded speech stimuli (saved as digital computer files) are presented through insert earphones using custom MATLAB software. Participants will make responses either by

pressing a button on an ELO TouchSystems touch screen monitor (for word testing) or by verbally repeating back the sentences (for sentence testing). The computerized auditory training program (Speech Perception Assessment and Training System; SPATS) will be run from a computer. The SPATS stimuli are digital computer files that are presented through insert earphones. Participants will make their responses concerning what they heard by mouse click or keyboard entry. At the end of each session, the response data will be stored on the local computer. No patient identifiable information will be included in the data files.

As part of the experimental set-up, all stimuli will be verified as to their spectral and temporal characteristics using a Tektronix oscilloscope and a Signal Analyzer. The stimulus intensity levels will be checked weekly using a Larson-Davis 824 sound level meter and a standard 2-cc coupler. Biologic calibrations will also be performed weekly, where study team members will listen to the sounds presented through earphones to ensure that the volumes are appropriate.

## **Testing Procedures**

### **Standard of Care Procedures**

At the beginning of the initial study visit (after informed consent is obtained), routine audiometric tests will be administered by trained Study Staff (primarily co-investigator [name], with assistance from Study Staff members [name] and [name] as needed). [name] and [name] are trained clinical audiologists with an advanced degree in audiology and are licensed to practice in either California or another state. This is the same requirement as for audiologists who work in the Audiology clinic at the VALLHS. [name] has over 30 years of experience testing human and animal subjects in auditory research settings. The purpose of this evaluation is to verify hearing eligibility for the study. If a participant recently had a hearing test at the VA Loma Linda audiology clinic (within 6 months), this audiometric information may be used for the study and so it may not be necessary to repeat the initial hearing screening for the study. The following standard-of-care procedures will be conducted:

**Interview:** An initial interview will be conducted to obtain case history information about current and past hearing and ear-related problems, family history of hearing loss, history of noise exposure, current health status, and present and past hearing-aid use (if any). The purpose of this history is to establish eligibility to be in the study, to aid in the interpretation of the experimental data, to provide case history information concerning probable etiologies of participants' hearing losses in articles and presentations emerging from the study.

**Otoscopy:** The ear canal and tympanic membrane of the patient will be visually inspected for abnormalities, such as earwax blocking the ear canal.

**Pure-tone audiometry.** Air conduction and bone conduction thresholds will be measured using recommended procedures (American Speech-Language-Hearing Association, 1978). Pure tone thresholds will be used to define degree and type of hearing impairment. Pure-tone audiometry will be repeated at visits 6, 11, and 12 to detect any changes in hearing thresholds over the course of the study (not due to participation in the study itself because all sound levels are presented at safe volumes).

**Speech audiometry.** Speech recognition thresholds will be measured using standard clinical procedures. Word recognition scores in quiet will be measured in each ear by presenting pre-recorded word lists through insert earphones and subjects verbally repeat back the words they hear. This information will be used to aid in the interpretation of the experimental data.

Immittance audiometry. Immittance audiometry will be used to examine middle ear function and to rule out conductive or retrocochlear pathology. Immittance audiometry will also be conducted immediately prior to TEOAE testing (described below) to ensure normal middle ear function.

### Experimental Procedures

The following experimental procedures will be conducted:

TEOAE Testing: The basic task of the participants is similar to TEOAE procedures used clinically to evaluate hearing function objectively. Testing involves listening to sounds presented through earphones while seated comfortably in a sound-treated booth, and remaining alert but quiet in order to successfully measure responses from the cochlea and brainstem. Excessive body movement, swallowing, coughing, talking, and chewing creates acoustic and electric noise that can obscure recordings of TEOAEs, so it is imperative that participants remain as still as they can during the measurements. The experimental measurements differ from clinical measurements primarily in the types of sounds presented, the data analysis, and the use of an attention task to keep participants alert and awake. Specially constructed stimuli intended to stimulate the MOC system will be generated digitally on a computer, and played out to the listener using high-quality digital-to-analog converters, attenuators, filters, and other laboratory equipment. These sounds involve amplitude-modulated tones, click trains, and white noise. All stimuli will be presented at moderate volumes that are well below sound levels considered hazardous by OSHA and NIOSH standards. TEOAE measurements consist of waveforms, which are changes in sound amplitude across time. MOC function will be quantified as the change in waveform amplitude with versus without white noise presented to the opposite ear, where a larger change indicates stronger MOC activity. Repeated measurements will be obtained (both within a study visit and across study visits) to determine the change in MOC activity across time. Immittance audiometry will be obtained immediately prior to TEOAE testing at each visit to ensure that middle ear function is normal (successful measurement of TEOAEs requires normal middle ear function).

Word/Sentence Testing: Testing involves listening to words and sentences presented through earphones while seated in the sound-treated booth. Speech stimuli will be presented in the presence of background noise. Participants make a response about the word(s) they heard. For word testing, participants press a button on a touch screen monitor corresponding to the words that they heard. Their responses are automatically recorded by custom software. For sentence testing, participants verbally repeat back the words they hear in each sentence. The experimenter enters the number of correct responses into the computer. The experimental measurements differ from clinical measurements primarily in the types of sounds presented and the data analysis. Sounds will be presented at safe and comfortable levels. Performance will be quantified as the number of words correct and also the characteristics of the stimuli (e.g., the levels of the speech and background noise). Repeated measurements will be obtained (both within a study visit and across study visits) to determine the change in speech perception ability across time.

Auditory Training (Experimental group only): Listeners will be seated comfortably in the sound booth at a workstation with a computer screen, keyboard, and mouse. Sounds will be presented to the participants through insert earphones. Sounds for the testing and training will be presented at calibrated levels from the computer. Participants will make their responses concerning what they heard by mouse click or keyboard entry. At the end of each

session, the response data will be stored on the local computer. No patient identifiable information will be included on the data files. Performance will be quantified as the number of correct responses and also the characteristics of the stimuli (e.g., the levels of the speech and background noise). The auditory training program consists of a curriculum of word and sentence presentations in various noise levels, and performance on repeated measurements are tracked throughout the subject's participation in the program.

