## **Participant Groups**

Participants will be randomly assigned *a priori* to either the Experimental group (auditory training) or Control group (no auditory training) using simple random assignment. Because the third group (Speech Group) is added after the experimental and control groups have completed their participation, to provide additional power to the regression analysis, the Speech group will be assigned by the investigator. Because this study will detect whether or not significant changes in MOC activity and speech perception across time occurred as a result of auditory training, the Control group is needed to establish the test-retest reliability of our outcome measures in the absence of any training. Participants will be informed of which group they are assigned to at the initial visit, but they will not be allowed to change groups.

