All participants will undergo otoscopy, immittance testing, TEOAE testing, word testing, and sentence testing at each visit. Participants in the experimental group will also complete the auditory training program, with baseline (pre-training) measures at visit 1, training occurring in visits 2-11, and visit 12 serving as the retention (post-training) measurements. These participants will therefore undergo a total of 15 hours of auditory training spread across 10 visits, plus pre- and post-tests. Pure-tone audiometry will be repeated for all participants at visits 6, 11, and 12 to detect any significant changes in hearing thresholds during the course of a participant's participation (not due to actual participation in the study because all sound levels will be presented at safe volumes). Such changes in audiometric measures are not likely to occur over this relatively short time period. All participants (except those in the Speech group) will be asked to return for a visit twice a week for the first 6 weeks (visits 1-11) and return for the final visit 4 weeks later (visit 12). Each subject will be allowed a maximum of two make-up visits in case a visit needs to be stopped early, resulting in a maximum of 14 study visits.

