### **Steps Taken to Minimize Risks and Data Safety Monitoring**

Participants will be provided with as many breaks during testing as they or the experimenter feel are helpful to minimize mental fatigue and boredom. Loudness levels of stimuli are carefully controlled, with frequent calibration and monitoring of laboratory equipment. Participant confidentiality will be protected by using only participant codes (three numbers) to label data collection sheets and computer data files. Participant numbers will be assigned sequentially and will not contain identifying information. Neither names nor social security numbers will be included in the participants' data files, although names and contact information will be filed separately so that participants can be contacted for future appointments. Signed consent forms will be stored separately from the experimental data as well. Any written or oral report or publication of the information obtained in this study will not contain the names of participants or identifying information. All data records will be stored on password-protected computers or as hard copy in locked offices or laboratories. Data are stored in the laboratory and/or in the experimenter's office, both of which are kept locked when no one is there.

Participant safety and comfort and data collection will be constantly monitored for each participant by the research team member collecting the data for that participant. Overall data collection will be monitored by the Principal Investigator, [name]. Following completion of the study, all data will be maintained in accordance with VHA guidelines.

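### Sentence scores are judged by an experimenter whom nothing in the plan keeps unaware of group; scorer masking at visits 1 and 12 is feasible and should be added.

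*Combined protocol and SAP*

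**What the plan says.** Experimental Procedures describes two speech tests that are scored differently. For words, participants press a touch screen and "Their responses are automatically recorded by custom software". For sentences the response is oral: "For sentence testing, participants verbally repeat back the words they hear in each sentence", after which "The experimenter enters the number of correct responses into the computer". No recording, second scorer or scoring rule is described.

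Participant Groups sets up the comparison as "Experimental group (auditory training) or Control group (no auditory training) using simple random assignment" and adds that "Participants will be informed of which group they are assigned to at the initial visit". There is no sham training.

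Order of Procedures gives every participant the same tests at each visit. It confines training to visits 2-11, makes visit 1 the baseline, and describes "visit 12 serving as the retention (post-training) measurements". The repeat audiometry at visit 12 is for everyone.

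Steps Taken to Minimize Risks and Data Safety Monitoring says that "data collection will be constantly monitored for each participant by the research team member collecting the data for that participant". It also provides for three-digit participant codes on data sheets and files, as a confidentiality measure. No section of the available document mentions masking of testers, scorers, TEOAE processing or analysts.

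**The concern.** Whether a repeated word counts as correct is decided by the person listening. If that person knows who has been trained, borderline responses may be credited differently in the two groups. Such a shift goes straight into the sentence change score. Randomisation does not remove it, because it arises after assignment. The Control group does not remove it either, because it is by definition a difference between the groups. Data Analysis uses Control-group test-retest data to decide what counts as a significant change, so any leniency towards trained participants would be judged against a threshold set by people who did not receive it.

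Sentence recognition is one of the three outcomes on which Sample Size is based, so this is not a peripheral measure. The exposure is also partly avoidable, because nothing planned at visits 1 and 12 requires the tester to know the group.

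**Working it through.** **1. The plan's own figure.** Sample Size gives a minimum of n = 11 for a paired pre/post difference in sentence recognition (type I error 0.05, 80% power). The underlying means and SDs are not given, so the figure cannot be reproduced. Solved backwards with a two-sided paired t-test, n = 11 corresponds to a standardised change of about 0.94 to 1.00. This point does not dispute n = 11, and masking would not change it.

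**2. Which outcomes are exposed.**
- Sentences: spoken response, counted and entered by the experimenter. Exposed.
- Words: touch-screen response, recorded by software. Not open to scorer judgement.
- TEOAE: instrumental recording, quantified as a change in waveform amplitude. Only undescribed processing choices, such as artefact rejection, could be influenced. This exposure is weaker.

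**3. Can the scorer know the group?** Participants know it from the initial visit, training is visible at visits 2-11, and no separate tester is provided for. The document allows the scorer to know; it does not say that the scorer always does.

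**4. Can visits 1 and 12 be masked?** The test battery is common to all, there is no training at either visit, and the audiometry at visit 12 is done in everyone. Planned content is therefore the same in the Experimental and Control groups.

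**5. Illustrative size.** Assume no true effect and a scoring shift of b SDs of the change score in trained participants only. The values of b are assumptions. For a two-sided 5% two-sample t-test on change scores with n per group, the noncentrality is λ = b√(n/2) on 2n − 2 degrees of freedom, and the false-positive rate is the probability that |t| exceeds the critical value. The values of n come from Sample Size: at least 12 and up to 20 per group.

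| n per group | b = 0.2 | b = 0.3 | b = 0.5 |
|---|---|---|---|
| 20 (√10 = 3.162) | λ = 0.632, 9.5% | λ = 0.949, 15.2% | λ = 1.581, 33.8% |
| 12 (√6 = 2.449) | λ = 0.490, 7.6% | λ = 0.735, 10.8% | λ = 1.225, 21.6% |

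For a paired pre/post test within the trained group, the comparison on which Sample Size rests, λ = b√n. The rates are 9.7%, 15.8% and 35.3% at n = 12, and 13.6%, 24.7% and 56.5% at n = 20. In both designs the inflation grows with n, so recruiting more participants would not cure it. With b = 0 every rate is 5%.

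For context, shifts of 0.2 and 0.5 are about one fifth and one half of the smallest change implied by n = 11 (0.2/0.94 = 0.21; 0.5/0.94 = 0.53).

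**6. Effect on the correlation.** Adding a constant c to every trained participant's sentence change leaves the within-group correlation with MOC change as it was: corr(X, Y + c) = corr(X, Y).

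**The case against.** The strongest objection is that masking two visits protects only part of the data. Speech testing takes place at every visit, and Data Analysis plans correlations over the course of training and repeated-measures analyses across visits. Scores from visits 2-11 would stay exposed, including visit 11, the last before the four-week gap. This stands. The fix protects the baseline-to-retention contrast and should claim no more.

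The size is also hypothetical. Data Analysis names no two-sample test on change scores, and nothing in the document supports any particular shift. This stands too: the figures show direction and scale and do not predict the actual bias.

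The staffing argument needs care. Standard of Care Procedures describes more than one trained tester, but for routine audiometry; the document does not say who runs the experimental tests. A rota among existing staff is plausible but not established.

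Two stronger readings are tempting. A reader might infer that the planned MOC-speech correlation must be biased. A uniform scoring shift does not alter a within-group correlation. It would matter only if leniency tracked each person's MOC change, or if the groups were pooled and also differed in MOC, and the document gives no ground for assuming either. A reader might also infer that the software-recorded word test should carry the speech conclusion. Words and sentences are separate outcomes with separate sample-size bases (n = 12 and n = 11), and a difference between them may be real.

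Finally, data files already carry ID codes only, so for the TEOAE the one new step is when group labels are merged.

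**Conclusion.** The point holds as an inexpensive improvement that should be made. A human-judged outcome is scored in an open, no-sham comparison with no stated masking, and group-dependent scoring could appear as a training effect. With no true effect, assumed shifts of 0.2 to 0.5 SD would raise a nominal 5% two-sample test on change scores to about 10% to 34% at 20 per group, or about 8% to 22% at 12 per group.

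The conclusion rests on the document's silence about masking, on scoring being done at the time of testing (no recording is described), and on assumed bias sizes and an assumed two-sided test. It concerns the Experimental and Control groups only. The Speech group is assigned later by the investigator and is exempt from the twice-weekly schedule. The document does not show that biased scoring will occur.

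**What to change.** In Order of Procedures, state that:
- sentence testing at visits 1 and 12 is run and scored by an existing team member who has not run that participant's training visits and is not told the group;
- the participant learns the group only after visit 1 testing is complete, from someone else (this still falls within the initial visit);
- participants are asked not to reveal their group to the tester.

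In Data Analysis, state that the visit 1 to visit 12 contrast is the scorer-masked sentence comparison, and that sentence scores from visits 2-11 are unmasked and will be read as such.

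As a minor addition, state that TEOAE artefact rejection and waveform processing are completed under the existing ID codes before group labels are merged.

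Cost: no added visit, test or participant. If existing staff share the testing, scheduling is less flexible at two visits. A tester-by-visit difference may arise in the repeated-measures analysis, but it would apply equally to both groups. Participant expectation remains, because participants know their group and there is no sham.
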